## Project Summary

The purpose of this pragmatic clinical trial is to transform care, reduce health risks, and improve outcomes for patients with chronic pain who are taking long-term prescription opioids. Our proposed study will address several critical evidence gaps that currently hinder patients and physicians from making informed decisions about pain care. This project will provide both patients taking opioids and their prescribers with the specific evidence needed to choose the most effective strategies for reducing opioid doses and minimizing pain, reducing pain interference, and improving role function.

For patients interested in reducing opioid use, we aim to: (1) reduce prescription opioid use while maintaining pain control; and (2) compare the effectiveness of the Chronic Pain Self-Management Program (CPSMP), cognitive behavioral therapy for chronic pain (pain-CBT), and no behavioral treatment, all within the context of patient-centered collaborative opioid tapering. The acronym EMPOWER stands for *Effective Management of Pain and Opioid-Free Ways to Enhance Relief*.

[Please note: Along with the EMPOWER randomized controlled trial, PCORI funded a separate sub-study involving a national observational study of people taking daily prescription opioids (not tapering). As this observational sub-study was not part of the randomized controlled trial, it is not described in this protocol.]

## Study Goals and Objectives

### *Aim 1: Reduce or Contain Prescription Opioid Use While Maintaining Pain Control.*

Hypothesis 1a. At one year, 40% of participants in the Taper Only group (no behavioral treatment) will successfully reduce prescription opioids by  $\geq 50\%$  in MEDD without worsening pain intensity, pain interference, or satisfaction with social roles and activities at 12 months.

Hypothesis 1b. Success with patient-centered opioid tapering will not be associated with the starting MEDD.

### *Aim 2: Compare the Effectiveness of (1) Taper + CPSMP, or (2) Taper + pain-CBT, or (3) No Behavioral Treatment (Taper Only) within the Context of Patient-Centered Collaborative Opioid Tapering.*

Hypothesis 2a. Participants receiving behavioral interventions (Taper + pain-CBT or Taper + CPSMP) will be more likely to reduce their opioid dose than those in the Taper Only group (no behavioral intervention).

Hypothesis 2b. There will be no significant differences in dosage reduction or the percentage of participants reducing dosage between the Taper + pain-CBT and Taper + CPSMP groups.

Hypothesis 2c. Participants in the Taper + pain-CBT group will experience less pain, less pain interference, and decreased depression compared to those in the Taper + CPSMP or Taper Only groups.

Hypothesis 2d. Participants in the Taper + CPSMP group will show greater improvements in satisfaction with social roles and activities and self-efficacy compared to those in the Taper + pain-CBT or Taper Only groups.

*Exploratory Hypothesis 2e.* Opioid escalation will be less common among participants in the behavioral intervention groups (Taper + pain-CBT or Taper + CPSMP) compared to those in the Taper Only group.

## Study Design

This is a pragmatic, prospective, longitudinal, multi-center, three-arm, randomized controlled clinical trial. The study will include 594 patients receiving daily prescription opioids in primary care and pain clinics at EMPOWER study sites (see Table 1 for a list of study locations).

[figure not shown]

## Methodology

At all sites, patient recruitment will occur through the following methods: identifying eligibility in medical records, in-house advertising, external community-based advertising, and use of the CHOIR database at Stanford University. Study coordinators will review the clinic schedule daily to identify eligible patients based on pain and opioid information available in the electronic medical record. Clinicians will discuss EMPOWER with patients and obtain permission from interested patients to be contacted by study staff. Study coordinators will then obtain informed consent and register participants in the CHOIR research learning health system database to initiate survey deployment. After completing the baseline survey, participants will be randomized to one of three intervention arms: (1) EMPOWER Taper Only (no behavioral treatment); (2) EMPOWER Taper + pain-CBT; or (3) EMPOWER Taper + CPSMP. Block randomization with variable block sizes, stratified by study site, will be utilized. The Executive Research Team, including the Principal Investigator and the data analytic team, will remain masked to intervention assignment throughout recruitment, enrollment, and data collection. Participants, EMPOWER clinicians, and study coordinators will be aware of intervention assignment. For the study flow diagram, see Figure 1.

**Figure 1. Study Flow Diagram**

**Eligibility Criteria.** Inclusion criteria are: adults aged 18–85 years, diagnosed with chronic non-cancer pain (lasting at least six months), and actively taking prescription opioids (at least 10 MEDD) for at least three months at any of our seven study sites. Eligibility will not be restricted to specific pain conditions. Exclusion criteria include: clinician-determined moderate or severe opioid use disorder (OUD) as defined by a brief screening tool; inability to provide informed consent; inability to meaningfully participate in group interventions (e.g., due to cognitive impairment or lack of English fluency); or known disruptive behavior that could interfere with the group learning experience and treatment outcomes for the cohort. Patients with moderate to severe OUD will be referred for addictionology consult or triaged per local systems.

Patients with active substance use disorder (SUD) may enroll and local systems will refer them for SUD evaluation and treatment as clinically indicated. No special vulnerable populations will be recruited (e.g., children or patients pregnant at the time of enrollment). All research procedures will take place at the seven clinical sites, with data collection and some treatment elements occurring online.

**Consent Procedures.** Electronic consent will be administered through CHOIR^1 following completion of the screening visit. Participants will provide consent by entering their full name and date on the consent form webpage in CHOIR after reviewing the form with study staff. A copy of the consent form will be securely emailed to the participant. Two study sites (Phoenix Veterans Affairs Health Care System and Kaiser Permanente Oakland) will administer consent locally.

**Participant Compensation.** Participants will receive a \$25 Amazon gift card code for completing assessments at baseline, month 6, and month 12, and \$5 for completing weekly surveys from weeks 1–24 and monthly surveys from months 7–11 (29 total surveys). Total possible compensation for study participation is \$220. For participants who do not complete their 12-month survey and do not respond to any of the contact attempts made by the study team including the EMPOWER clinician we will offer an additional \$50 incentive for completing the last survey.

**Learning Health System and Informatics Platform.** CHOIR (<https://choir.stanford.edu/>) is an electronic informatics platform that serves multiple study functions. It is a secure (password-protected), HIPAA-compliant platform hosted by the Stanford University School of Medicine. CHOIR will collect patient-reported data at each time point using surveys tailored to the study and will be standardized across all study sites. Additional CHOIR functions include obtaining online consent, automated post-enrollment randomization, deployment of tailored surveys based on treatment arm assignment, a patient-reported outcomes data system that minimizes response burden using computer adaptive testing for NIH PROMIS measures, a centralized study database, an automated electronic payment system for survey completion, real-time display of patient progress for study clinicians, generation of personalized opioid tapering plans, monitoring for patient adverse events, and deployment of alerts to various stakeholders to address patient risks, minimize missing data, and manage participant payments. Clinicians will be able to view individual patient progress and longitudinal data in real time. Paper surveys will be mailed to participants who lack access to email, computers, or smartphones, and study staff will input the data into the electronic database.

***Weekly CHOIR surveys:*** All patients will receive weekly CHOIR e-surveys via email to assess taper discomfort symptoms or other issues, with the explicit purpose of informing clinical care, symptom triage, and any necessary adjustments to their taper plan. Taper-related symptoms of moderate severity will trigger an automated e-alert to the prescriber, study site director, site coordinator, and study manager. Patients will also receive automated e-response messages with recommended actions, such as calling the clinic for telephone triage or scheduling an in-clinic visit. At each follow-up visit, taper discomfort symptoms will be reviewed and confirmed by the prescribing clinician as either related or unrelated to the taper. Moderate and severe symptoms will be reported to the local IRB, the Data Safety and Monitoring Board (DSMB), and the study sponsor.

***Monthly CHOIR surveys:*** Patients will be assessed monthly for satisfaction with the study, current opioid use, hospital or emergency medical visits, depressive symptoms, suicidality, and other factors that may indicate symptom worsening and require follow-up. Suicidality will trigger e-alerts to the prescribing clinician, site director, site coordinator, study manager, and the overall principal investigator. Site-specific messages will provide patients with instructions for non-emergency triage (e.g., calling the clinic for telephone or in-person follow-up) and emergency triage options in their community (e.g., calling 911), rapid contact with clinic staff, and crisis hotlines.

Weekly and monthly surveys will ensure careful monitoring of patients, triage of issues, and close connections with study staff and prescribing providers to enable rapid taper adjustments and address any additional needs. Study clinicians may securely access EMPOWER CHOIR via a web browser to review patient responses and coordinate participant activities. Comprehensive patient-reported survey batteries will be administered at baseline and at six and 12 months, including data on opioid use.

***Randomization.*** Each site will conduct a site-specific randomized controlled trial using a randomized design, allowing rapid accrual of patient cohorts (N=8–18 per cohort) assigned to the same intervention arm and timely delivery of behavioral interventions. Patients entering the study will be automatically assigned to the currently open intervention arm. The ordering of intervention arms will remain blinded to patients and clinicians, who cannot choose or direct group assignment. Study coordinators, while unblinded, will be trained to maintain clinician and patient blinding. After enrollment and baseline measures, group assignments will be revealed to participants. A statistician unaffiliated with patient care will create unique randomization schemes for each site, enabling prompt receipt of behavioral interventions for those assigned to such arms (ideally within two to ten weeks of taper initiation). Behavioral intervention timing will be recorded.

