#### *Study Arms*

**(1) EMPOWER Taper + Cognitive Behavioral Therapy for Chronic Pain (pain-CBT).** Pain-CBT is a behavioral treatment that reduces chronic pain and its impacts through patient education, skills acquisition, and social support. Research on pain-CBT indicates benefits for reducing pain intensity, pain catastrophizing, depression, and the social impact of pain. CBT is considered the gold-standard psychobehavioral treatment for pain, with other behavioral treatments demonstrating non-inferiority but not superiority. A general pain-CBT therapist manual and corresponding patient workbook were developed for the EMPOWER study (EMPOWER CBT). A relaxation MP3 audio file accompanies the patient workbook. Consistent with general pain-CBT, the EMPOWER CBT protocol includes interactive discussion, pain education, relaxation training practice, goal setting, cognitive restructuring, problem-solving, and action planning, with home exercises incorporated into each session. Participants will learn to effectively manage their pain and symptoms while working towards achieving the goals that matter to them. A mental health will deliver the eight-week group intervention to cohorts of patients (N=8–18) assigned to this arm. Intervention sessions will be delivered weekly and last two hours. To ensure consistency across all study sites and cohorts, therapists will be trained in the common eight-session CBT protocol, with competency assured by Director [name]. The structured format of the CBT intervention ensures treatment fidelity, with the trained therapists using PowerPoint slides (for didactic content), corresponding worksheets from the participant workbook, and optional reading from an additional book. The study coordinator will be present at each treatment session and facilitate intervention fidelity by ensuring participants have corresponding materials, including the relaxation audio. Participants assigned to this intervention arm will not receive CPSMP during the study period. No other aspects of pain care will be constrained.

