**(2) EMPOWER Taper + The Chronic Pain Self-Management Program (CPSMP).** CPSMP is an evidence-based behavioral treatment delivered by two certified healthcare clinicians or peer co-leaders with lived experience in successful pain self-management. Certification as a CPSMP leader requires 24 hours of training over four days. The CPSMP manualized protocol includes patient education about pain and strategies for effective self-management of pain, its impacts, and other symptoms. Based on self-efficacy theory, CPSMP is delivered in six weekly 2.5-hour group sessions to cohorts of 8–18 participants. All participants receive a book on pain self-management and an exercise CD. Like pain-CBT, CPSMP incorporates interactive discussions, relaxation training, action planning, and home exercises into each session. Patients learn to live better with chronic pain by making daily choices that support improved health and function. Participants assigned to this arm will not receive group pain-CBT during the study period. No other aspects of pain care will be constrained, including individual psychological treatment; receipt of non-study treatments will be tracked.

Prior research has shown that pain-CBT and CPSMP have both shared and distinct effects, suggesting some individuals may respond better to one treatment than the other. However, no evidence currently exists to guide a best-practice choice between the two. While pain-CBT and CPSMP are both effective for chronic pain, they have not been tested within an active opioid reduction protocol. We hypothesize that these behavioral interventions will help patients reduce opioids and associated risks, manage pain, and restore function in ways superior to opioid reduction alone.

**(3) EMPOWER Taper Only (usual care).** Participants assigned to this intervention arm will participate in the voluntary EMPOWER patient-centered opioid tapering program and will not receive group pain-CBT or CPSMP during the 12-month study period. No other aspects of pain care will be constrained.

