#### **Virtual Format for Behavioral Treatment Groups**

**Background:** In March 2020, the COVID-19 pandemic led to social distancing safety requirements, which prevented the continuation of in-person delivery of our behavioral treatment groups. In response, with PCORI approval, we demonstrated the feasibility of virtual groups by piloting a virtual option with participants who were already enrolled in the study (i.e. enrolled prior to 03/26/2020). We now offer virtual (live, online) delivery of our behavioral treatment groups as another option for all participants including new enrollments. Due to ongoing and unpredictable COVID-19 restrictions on group gatherings, live virtual treatment delivery is essential to ensure successful completion of our RCT.

Content: Virtual pain-CBT and CPSMP treatments are delivered exactly as outlined in the protocol where the same content and materials (e.g., participant workbooks, presentation slides, etc.) by live facilitators with live participants. The only difference between virtual and in-person is the video format in the virtual groups and materials are distributed via traditional mail instead.

Platform – Each site delivers the virtual treatments using a HIPAA compliant and secured platform endorsed by their respective institution (Zoom at Stanford and Colorado, VA Video Connect at the Phoenix VA, and WebEx at Intermountain Health). The platforms are broadly utilized for telehealth at the sites.

Facilitator Training – To assure high-quality and standardized delivery, the facilitators who conduct the in-person groups at each site, are also the same facilitators delivering the virtual treatments. Additionally, we centralized our virtual system across Stanford Pain, Stanford Primary Care and Colorado where we have Stanford psychologists (or Telligen peer leaders) leading a cohort comprised of both Stanford and Colorado participants. As closed payer systems, Phoenix VA and Intermountain Health do not permit external services. The facilitators practiced delivering the programs on the virtual platform up to three times before the start of the first series.

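### Group delivery of pain-CBT and CPSMP is ignored in the between-arm power, precision and tests (H2a–H2d), and the unit of allocation is not stated

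*Combined protocol and SAP*

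**What the plan says.** Delivery. Under Study Arms, a therapist "will deliver the eight-week group intervention to cohorts of patients" numbering 8–18, and "CPSMP is delivered in six weekly 2.5-hour group sessions to cohorts of" the same size. Taper Only participants "will not receive group pain-CBT or CPSMP during the 12-month study period". The paragraph on virtual groups in the Statistical Analysis Plan puts the usual group size, in person and virtual, at about 4. Some virtual groups cross sites, with facilitators "leading a cohort comprised of both Stanford and Colorado participants".

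Allocation. The opening of Methodology says: "Block randomization with variable block sizes, stratified by study site, will be utilized". The informatics paragraph lists "automated post-enrollment randomization" among the platform's functions. The Randomization paragraph has each site accrue cohorts of 8–18 "assigned to the same intervention arm and timely delivery of behavioral interventions", and adds: "Patients entering the study will be automatically assigned to the currently open intervention arm".

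Sizing and analysis. Sample Size Calculations and Study Power gives, at 163 per arm, 80% power for 40% v 53.5% (H2a), an expected 95% CI of ±11 points (H2b) and 80% power at 0.311 SD (H2c, H2d). It states no ICC or design effect. The Statistical Analysis Plan names chi-square and Fisher's exact tests, logistic regression, 95% CIs, t-tests, analysis of covariance and a repeated-measures mixed model whose only stated correlation is within subject. The adjustment covariates are not listed, so site is unspecified rather than excluded.

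**The concern.** Patients who share a facilitator and a group can have correlated outcomes. The protocol allows for this itself: Eligibility Criteria excludes people whose behavior could harm the group's treatment outcomes. With a positive within-group ICC that is not offset elsewhere, tests that assume independence reject too often, a valid analysis has less power than stated, and the H2b interval is too narrow. The H2b interval is to be read for equivalence, so the error there favours the claim. The sample-size section says the calculation rests primarily on the comparative-effectiveness aims, so these are the contrasts the trial was sized for.

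The unit of allocation decides how far the problem reaches. If patients are individually randomized, only the two behavioral arms are grouped and H1a and H1b are untouched. If whole cohorts are allocated, Taper Only may be correlated by cohort and period as well, and H1a could be affected.

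**Working it through.** **Inputs from the documents.** 163 analysed per arm; H2a 40% v 53.5%; H2b 50% in both arms; H2c/H2d 0.311 SD; two-sided 0.05; group size m of about 4 (reported) or 8–18 (planned); 594 enrolled, so 198 per arm. **Assumed.** ICC 0.01–0.05, because the documents give none. Each range below runs from ICC 0.01 to 0.05.

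**Step 1: reproduce the plan with independent patients.**
- H2a, pooled behavioral arms v Taper Only (326 v 163), pooled-variance test: 80.7%. A 163 v 163 comparison gives only 68.7%, so the stated 80% refers to the pooled contrast.
- H2b: 1.96 × √(2 × 0.25/163) = 10.9 points.
- H2c/H2d: noncentral t, df 324, ncp = 0.311/√(2/163) = 2.81, power 79.9%.

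All three match the stated figures with a design effect of 1.

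**Step 2: pain-CBT v CPSMP, grouped in both arms.** DEFF = 1 + (m − 1) × ICC. Power uses ncp = 0.311/√(2 × DEFF/163). Unadjusted type I error = 2 × [1 − Φ(1.96/√DEFF)]. H2b half-width = 1.96 × √(0.5 × DEFF/163).

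Example, m = 4 and ICC 0.05: DEFF = 1.15; ncp = 2.62, power 74.2%; 1.96/√1.15 = 1.83, error 6.8%; half-width 11.6 points.

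| m | DEFF | Power at 0.311 SD | Unadjusted type I error | H2b half-width (points) |
|---|---|---|---|---|
| 4 | 1.03–1.15 | 78.8%–74.2% | 5.3%–6.8% | 11.0–11.6 |
| 8 | 1.07–1.35 | 77.2%–67.3% | 5.8%–9.2% | 11.2–12.6 |
| 13 | 1.12–1.60 | 75.3%–60.0% | 6.4%–12.1% | 11.5–13.7 |
| 18 | 1.17–1.85 | 73.5%–53.9% | 7.0%–15.0% | 11.7–14.8 |

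Actual coverage of the unadjusted H2b interval is 100% minus the error column: 94.7%–93.2% at m = 4. In groups of 4 the half-width still rounds to 11 points up to an ICC of about 0.04.

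**Step 3: contrasts with Taper Only, patients individually randomized.** DEFF applies to the behavioral side only.
- H2a power: 80%–79% at m = 4, 79%–73% at m = 13.
- H2a chi-square error: 5.1%–5.6% and 5.5%–7.4%.
- H2a Fisher error (beta-binomial simulation; 4.5% with no clustering): 4.5%–4.9% and 4.8%–6.5%.
- One behavioral arm v Taper Only at 0.311 SD, ncp = 0.311/√((1 + DEFF)/163): power 79%–77% and 78%–69%.

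**Step 4: contrasts with Taper Only, whole cohorts allocated and Taper Only with the same ICC.**
- H2a power: 80%–75% at m = 4, 76%–61% at m = 13.
- H2a chi-square error: 5.3%–6.8% and 6.4%–12.1%, the same as pain-CBT v CPSMP.
- H2a Fisher error by simulation: at m = 4 about 5% at ICC 0.01–0.02 and about 6% at 0.05; at m = 13 about 6%–11%.
- H1a: the exact rule (at least 79 successes in 163, nominal upper tail 2.5%) has true upper-tail error 1.7% under independence, 1.9%–2.4% at m = 4 and 2.4%–4.8% at m = 13.

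**Step 5: offset from site.** Allocation is stratified by site. If outcomes vary by site and the test ignores it, the unadjusted variance is too large, which works against the inflation. A t-test simulation with seven sites balanced by arm, groups nested in site and an assumed site ICC of 0.05 gives type I error of 4.9%, 5.2% and 6.3% at group ICC 0.01, 0.02 and 0.05 in groups of about 4. In groups of about 12 it gives 5.8%, 6.9% and 10.9%. The simulation does not represent virtual groups that cross sites.

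**The case against.** The strongest reply is that delivered groups average about 4, not 8–18. At that size the loss is small at a low ICC, and Step 5 shows that unmodelled site variation can bring the error back to nominal at ICC 0.01–0.02. This stands: the large figures at 13 or 18 describe the plan's stated group sizes, not the reported ones. It does not remove the omission, because 8–18 remains the specified size and the plan gives no figure for either.

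A reader might infer that pain-CBT v CPSMP is always the most exposed contrast. That holds only if patients are individually randomized. Under cohort allocation with a common ICC, the Taper Only contrasts are equally exposed (Step 4). Likewise, Fisher's test for H2a stays below 5% in groups of 4 only if Taper Only is unclustered.

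A reader might also infer that the two allocation descriptions are contradictory, or that this is a cluster-randomized trial. The documents support neither. Site-specific schemes agree with site stratification, and variable blocks could be cohorts of varying size. It may be one under-described scheme, but the unit is still not stated.

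Finally, one might infer that H2b would wrongly conclude equivalence. No margin is given, so nothing can be said beyond the interval being too narrow. It is also fair that Study Outcomes labels the Aim 2 outcomes secondary, and that H1a is unaffected if patients are individually randomized.

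**Conclusion.** The omission is clear from the documents: group delivery in two arms, power and precision that reproduce under independence, and no group term in any between-arm analysis. Its size is not known, because every ICC used here is assumed.

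For pain-CBT v CPSMP, which is grouped in both arms under either reading of allocation, the effect in groups of about 4 is modest. In groups of 8–18 it is material except at the smallest sizes and ICCs. The Taper Only contrasts are less affected if patients are individually randomized, and equally affected if cohorts are allocated and Taper Only shares the ICC. The plan's delivery-mode covariate, COVID analyses and attendance regressions do not address within-group correlation. This should be fixed, but it does not by itself invalidate the trial. Confidence is high in the omission and lower in the size of the harm.

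**What to change.** 1. Reconcile the opening of Methodology with the Randomization paragraph and state whether the patient or the cohort is allocated.
2. Keep a treatment-group or cohort identifier for every patient. None is documented; intervention timing and attendance are recorded, so it can be confirmed or rebuilt from those.
3. Analyse H2a–H2d with a mixed or GEE model that has a treatment-group effect, site as the stratification factor and a small-cluster correction, and that allows virtual cohorts crossing sites. If patients are individually randomized, make the group effect partially nested for Taper Only contrasts. If cohorts are allocated, put a cohort effect in all arms, extend it to H1a, and add enrolment period as a sensitivity analysis.
4. Restate H2a, H2c and H2d power and the H2b interval width over a stated ICC range, first for groups of about 4 and then for 8–18.

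Cost: SAP wording, a different model call and the work of confirming the identifier; no extra patients. At 4 per group there are about 198/4 ≈ 50 groups per arm, enough for a group effect. At 13 there are about 15 per arm, or roughly 2 per site with equal enrolment over seven sites, so enrolment period may not fit in the same model. Intervals will be somewhat wider and the stated power less favourable.

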***Access and Intervention Participation.*** The comparison across interventions will be performed according to the intention-to-treat principle. Additional comparisons based on the actual intervention received will be conducted as a sensitivity analysis. We will also study the effect of intervention participation and on treatment outcomes. To this end, we will perform regression analyses to examine the association between the success rate for opioid weaning and other outcomes with session attendance for the pain-CBT and CPSMP arms, separately, while adjusting for identified confounding factors affecting compliance. We will also investigate how baseline factors, such as socioeconomic status, affect the level of compliance.

***Virtual Behavioral Treatment Groups: Comparison of participants who receive in person vs. virtual treatment -*** We will examine mode of delivery as a potential covariate in our analytic models, and study statistician [name] will both advise and implement. Outside of this issue of treatment delivery mode, we must also recognize that COVID itself has introduced a new variable in the study. We will be examining COVID impacts, as well. In regards to the group size and effectiveness of the intervention, the size of the virtual groups are comparable to the size of the in person groups where most groups have an average size of 4 participants. Facilitators stated larger groups (more than 4 participants per cohort) usually provide a more dynamic experience with diverse interactions. While in smaller groups, participants have a chance to go into more detail regarding the skills they are learning and using and any barriers that arise.

***Sensitivity Analysis.*** We will perform sensitivity analyses to account for missing data and non-completion of behavioral interventions. In addition, we will consider an alternative definition of taper success, replacing the 50% reduction in opioid dose with a 30% reduction in opioid dose. A 30% change has been cited as a benchmark for a moderately clinically important difference in the chronic pain literature. Similar analyses will be conducted with this new endpoint as part of the sensitivity analyses.

Statistical analysis will be completed using SAS Enterprise Guide Version 8.3 and R Version 4.1.1.

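### The two accounts of randomization need reconciling; if sites fill one arm at a time, the Aim 2 comparisons should adjust for site and enrollment time, which the SAP does not name

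*Combined protocol and SAP*

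**What the plan says.** **Two descriptions of allocation.** The first paragraph of Methodology states: "Block randomization with variable block sizes, stratified by study site, will be utilized". The Randomization paragraph in the same section describes a site-level scheme "allowing rapid accrual of patient cohorts (N=8–18 per cohort) assigned to the same intervention arm" and adds: "Patients entering the study will be automatically assigned to the currently open intervention arm". It also says that "A statistician unaffiliated with patient care will create unique randomization schemes for each site". Neither description makes calendar time a stratum. Neither says whether the order in which arms open is restricted.

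**A change during enrollment.** The section on the virtual format says: "In March 2020, the COVID-19 pandemic led to social distancing safety requirements, which prevented the continuation of in-person delivery of our behavioral treatment groups". Virtual groups were piloted in patients enrolled before 26 March 2020 and then offered to new enrollees, so recruitment ran on both sides of the change. The section on virtual taper visits says that video appointments became easier to obtain from March 2020, in all arms.

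**The analysis.** For Aim 2 the SAP lists Chi-square or Fisher tests, t-tests, logistic regression and analysis of covariance on baseline covariates that it does not list, and a repeated-measures model. None names site or enrollment time. The SAP acknowledges that "COVID itself has introduced a new variable in the study", says that COVID impacts will be examined, and treats delivery mode as a possible covariate. It gives no COVID variable, date or model for the arm comparisons.

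**The concern.** When every new patient at a site goes to one open arm, neighbouring patients in time share an arm. Balance over time then depends on the order of a few runs, not on many individual assignments. If outcomes drift or step during enrollment, the imbalance multiplied by the size of the step enters the estimated arm difference. A test that treats patients as independently assigned does not allow for this extra variation.

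The comparisons at stake are Hypotheses 2a–2d. Depression (2c) and satisfaction with social roles (2d) are plausibly sensitive to distancing. The SAP's existing text does not close the gap. Delivery mode of the groups is settled after assignment and does not exist in Taper Only, so it cannot adjust a comparison with that arm.

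**Working it through.** **1. The plan's own figure.** Sample Size Calculations and Study Power gives 80% power for 40% v 53.5% with 163 per arm. Take 2a as 163 Taper Only v 326 pooled behavioral patients:

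- Pooled rate = (163 × 0.40 + 326 × 0.535)/489 = 0.49.
- Null SE = √[0.49 × 0.51 × (1/163 + 1/326)] = 0.0480.
- Alternative SE = √(0.24/163 + 0.2488/326) = 0.0473.
- z = (0.135 − 1.96 × 0.0480)/0.0473 = 0.87, so power is 80.7%.

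The figure reproduces. It treats patients as independent and has no period term.

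**2. How often each arm opens.** Inputs are 594 patients (Sample Size section), seven sites (Eligibility Criteria: "All research procedures will take place at the seven clinical sites") and cohorts of 8–18 (mean 13).

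- 594/7 ≈ 85 patients per site.
- 85/13 ≈ 6.5 runs per site, and 6.5/3 ≈ 2 openings per arm per site.
- With runs of about 4, the average group size in the SAP's virtual-groups paragraph: 85/4 ≈ 21 runs, or about 7 openings per arm per site.

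**3. Chance imbalance in the share enrolled after a break.** This was simulated with seven equal sites, 594 patients and the break at half of enrollment. Entries are SD (95th percentile of the absolute difference), in percentage points.

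| Allocation | Behavioral v Taper Only | Pain-CBT v CPSMP |
|---|---|---|
| Runs 8–18, order permuted in threes | 8 (15) | 9 (18) |
| Runs 8–18, order unrestricted | 16 (30) | 18 (35) |
| Runs of about 4, either order | SDs of 4–10 over both contrasts | |
| Individual, simple | 4 | 5 |

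Individual assignment in blocks brings the SD to about 1. Letting the break vary between sites by ±20% of enrollment raises the permuted SD for behavioral v Taper Only from 8 to about 10. Using 489 completers as well gives 12 (and 17 unrestricted).

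**4. Shift in the estimate.** Shift = imbalance × period effect. Assume a 15-point drop in success (57.5% to 42.5%).

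- 2a at the 95th percentile: 0.15 × 15 ≈ 2 points permuted, and 0.30 × 15 = 4.5 points unrestricted. The design difference is 13.5 points.
- 2b: 0.18 × 15 = 2.7 and 0.35 × 15 ≈ 5 points. The planned half-width is 11 points.
- 2c and 2d: a period effect of d SD shifts a pairwise difference by 0.18d to 0.35d. The detectable difference is 0.311 SD.

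**5. Type I error of the unadjusted 2a test.** All 594 are analyzed, 396 v 198.

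- Variance the test assumes: 0.25 × (1/396 + 1/198) = 0.001894, so SE = 0.0435.
- Within-period variance: 0.575 × 0.425 × (1/396 + 1/198) = 0.001851.
- The true variance adds (0.15 × SD of imbalance)².

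| SD of imbalance | True SE | 1.96 × 0.0435/true SE | Type I error |
|---|---|---|---|
| 0.08 | 0.0447 | 1.91 | 5.6% |
| 0.16 | 0.0493 | 1.73 | 8.3% |
| 0.04 (runs of about 4) | 0.0434 | 1.96 | 5.0% |
| 0.10 (runs of about 4, upper end) | 0.0456 | 1.87 | 6.1% |

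Simulation agrees: about 6% permuted, 8–9% unrestricted, and 5–6% with runs of about 4.

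**6. Other period effects, and adjustment.** With 489 completers, 40% mean success and runs of 8–18:

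| Period effect | Permuted | Unrestricted |
|---|---|---|
| None | 4.9% | 4.8% |
| 10 points | 5.9% | 6.9% |
| 20 points | 7.0% | 11.0% |
| 30 points | 11.0% | 15.5% |

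A Cochran-Mantel-Haenszel test stratified by site and period gave 4.4–5.6% in all of these. Individual block randomization with a 20-point step gave 4.7% without adjustment.

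**The case against.** A reader might infer that arm is confounded with the pandemic, so that the Aim 2 results are biased. The documents do not support that. A statistician outside patient care draws each site's scheme, so the expected imbalance is zero and no arm is favoured in advance.

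Several further objections have force:

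- **Blocking.** The block-randomization sentence may mean that individual patients are assigned in blocks, in which case the problem nearly disappears. It may instead mean that arm order is blocked, in which case the unrestricted figures do not apply. This stands, and it is why reconciling the two descriptions comes first.
- **Run length.** The SAP reports groups averaging about 4. If runs were that short, type I error is near nominal. Group size may understate how many patients were assigned in a run, and the protocol still plans 8–18, so this is not conclusive.
- **Size of the break.** Virtual groups kept the same content, visits stayed in-person or virtual by choice, and the protocol calls the move to telehealth smooth. The documents give no period effect, so 15 points is purely an assumption.
- **Existing provisions.** Baseline covariates will be adjusted for, and a COVID-19 impact survey is collected from baseline. Enrollment time could be among the covariates, but the SAP does not say so and gives the survey no role in the arm comparisons.
- **A single cut at 26 March 2020 is a poor measure.** Patients enrolled in the preceding year have their 12-month outcome after the change, yet would be coded as before it. This stands and shapes the fix.

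**Conclusion.** The point holds as a prespecification gap of modest size. The protocol gives two accounts of allocation that must be reconciled. Under the open-arm account, chance imbalance in calendar time is larger than individual randomization would give, and the named analyses do not allow for it.

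Under the assumed 15-point effect, the unadjusted type I error for 2a is about 6% (order permuted in threes), 8–9% (unrestricted), or 5–6% (runs of about 4). Larger period effects raise it and smaller ones make it negligible. The figures rest on equal sites, a break near mid-enrollment and a step at the date of enrollment; the documents give no enrollment dates. Real exposure would build up over follow-up instead of switching at entry.

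Hypothesis 1a is a single-arm test against 40% and is not affected. Correlation of outcomes within a treatment cohort is a separate matter and is not in these figures.

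**What to change.** 1. **Reconcile the two Methodology descriptions.** State whether the patient or the cohort is the unit assigned, and whether the order of arms within a site is blocked.
2. **Make the main comparisons for 2a–2d adjusted** for site, which is already the stratification factor, and for calendar time of enrollment. Use finer periods than one cut: for example, enrolled before late March 2019, late March 2019 to 26 March 2020, and after. If a period is thin, use calendar time within site.
   - For taper success (2a, 2b), use Cochran-Mantel-Haenszel or logistic regression, with a matching stratified interval for 2b.
   - For 2c and 2d, put site and period terms in the repeated-measures models. Let period interact with visit: baseline is one of the dependent measurements, so a main effect alone would not adjust the change from baseline.
3. **Report arm-by-period counts by site.**
4. **If runs remain unopened,** restrict each site's order so that every three consecutive runs contain all three arms. This does nothing for runs already filled; items 1–3 do not depend on it.

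The cost is SAP wording and a few extra model terms. Enrollment date precedes assignment, so adjusting for it introduces no bias. Fixing the terms in advance also removes the choice of whether to adjust for period after results are seen.
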